Target	
RNOH Anaesthetic MDT: Approximately 20 staff taking part in MDT meeting taking part in the MDT meeting preparation and discussion. We aim to collect data for approximately 40 cases discussed without the Salutare One Referral software and approximately 40 patients discussed with Salutare One Referral.
 
Royal Free (Colorectal Cancer): Approximately 20 staff taking part in MDT meeting taking part in the MDT meeting preparation and discussion. We aim to collect data for approximately 120 cases discussed without the Salutare One Referral software and approximately 120 cases discussed with Salutare One Referral.
 
Royal Free (Breast Cancer): Approximately 50 staff taking part in the MDT meeting preparation and discussion. We aim to collect data for approximately 150 cases discussed without the Salutare One Referral software and 150 patients discussed with Salutare One Referral. (Note: The Royal Free Breast Cancer MDT testing is currently on hold, subject further discussions).
	
Inclusion criteria (Active Study Group)	MDT meeting Panel Members, Coordinators and staff submitting MDT referrals will take part in this study.	
Exclusion criteria (Main study)	MDT meeting Panel Members, Coordinators and staff submitting MDT referrals who are unwilling or unable to take part in the study.	
Duration of study	
The study consists of 4 phases:
 
 1. Pre-intervention period (before-study control) with no access to the Salutare One Referral software. 2. Onboarding period to allow for software installation and staff training and adjustment to the technology 3. Salutare One Referral intervention period 4. Post-intervention period (after-study control) with no access to the Salutare One Referral software 
The total duration of the study will depend on the frequency of MDT meetings and the number of cases discussed.
	

	
 • Stanmore Anaesthetics MDT and Royal Free Colorectal Cancer MDT: The study duration will be approximately 18 weeks (4-week pre-intervention period, 2-week onboarding period, 8-week intervention period, 4-week post-intervention period) • Royal Free Breast Cancer MDT: The study duration will be approximately 10 weeks (2-week pre-intervention period, 2-week onboarding period, 4-week intervention period, and a 2-week post-intervention period). 
Additionally, 4 weeks are allowed to complete the study data collection.

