The RNOH Orthopaedic MDT meets every two weeks, with approximately 10-11 participants, including Anaesthetists, General Physicians, Medical Consultants, Rehabilitation Specialists, Cardiologists, and as needed, Orthopaedic Surgeons, Pharmacists, Haematologists and Radiologists. The MDT is chaired by [name], Consultant Anaesthetist, the study Principal Investigator. The MDT focuses on discussing complex surgery cases referred by Consultant Anaesthetists, primarily for cancer (e.g. sarcoma) and cardiovascular disease. Each case undergoes team discussion facilitated by a pre-assessment document.

At present, the MDT operates without specialised software, relying on completed documents uploaded to a Shared Drive. Typically, Consultants submitting referrals will circulate a Power Point slide deck, explaining the case being reviewed. A standard form is also completed and submitted. Administrative responsibilities are shared between a

Title: Salutare Dialogue for MDTs					
Authors	[name], [name], [name]	Ver.2		Date Authorised	22/01/2025

Registrar and the MDT Chair due to the absence of an MDT administrator. A notable time-consuming task involves soliciting comments from various specialists, such as Cardiologists, to ensure thorough evaluation of the patient. The MDT typically addresses a maximum of 10 complex cases per session. Approximately 20% of cases necessitate re-presentation due to missing critical information, such as comorbidities and medication, resulting in delays in patient pre-operative pathways.

Royal Free Colorectal Cancer MDT

The Royal Free Colorectal Cancer MDT convenes weekly, reviewing approximately 30 cases. The team comprises MDT Coordinators, Colorectal Surgeons, Oncologists, Radiologists, Pathologists and Clinical Nurse Specialists. The MDT focuses on discussing complex colorectal cancer cases and findings from surgical procedures, with approximately 50% of cases presented post-surgery. Each case discussion averages 10 minutes, with surgeons typically attending in person. Case submissions are managed through a combined effort between MDT Coordinators and Surgeons.

At present, the MDT operates using paper-based documentation. Cases are recorded on standardized forms, with referrals managed jointly by Consultants and the MDT Coordinator. Cases require comprehensive documentation of imaging, pathology, and clinical findings to enable effective team discussion and treatment planning.

Royal Free Breast Cancer MDT

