8.5 Statistical Analysis

This study will employ a descriptive approach to analyse the collected data. Prior to finalising the statistical approach, the distribution of key variables will be assessed. In cases where variables show significant skewness, data transformation techniques, such as logarithmic transformation, will be considered to improve normality.

Patient records discussed by the MDT panels will be reviewed and analysed. For the complex case MDTs (RNOH Anaesthetics MDT and Royal Free Colorectal Cancer MDT), all cases discussed during the study pre-intervention, intervention and post-intervention phases will be included in the study analysis.

For the high-volume MDTs (Royal Free Breast Cancer MD), approximately 25% cases are expected to be submitted using Salutare One Referral during the intervention period. A formal comparison of the pre-intervention and intervention study cohort will be made. At the end of the study, raw data will be processed for summary and descriptive statistics. The distribution of times from referral to MDT decision & implementation will be assessed to check if mean or median most appropriate to use.

Normally distributed data will be reported as means with 95% confidence intervals (CIs), while non-normally distributed data will be presented as medians with interquartile ranges (IQRs). Categorical variables will be summarized using proportions or percentages, accompanied by their corresponding 95% CIs.

Pending normality testing using the Kolmogorov-Smirnov Test, a combination of Multivariate Mixed-Effects Models and Generalized Linear Mixed Models (GLMMs), the latter for categorical, ordinal, and binary measures, will be carried out for comparing the system usability scales the acceptance of the null hypothesis.

Title: Salutare Dialogue for MDTs					
Authors	[name], [name], [name]	Ver.2		Date Authorised	22/01/2025

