10.3. Intervention phase

The study intervention involves NHS staff interacting with the Salutare One Referral software. The interaction with the One Referral digital tool is classed as and evaluated as a 'digital health intervention'. The term, 'digital health intervention' - first used in the field of digital therapeutics to describe diagnosis, treatment and monitoring of health conditions using software and digital applications (FDA, 2022) - has more recently been expanded to cover the use of information and communication technology (ICT) in support of health and health-related fields, encompassing emerging areas such as the use of advanced computing sciences in big data, genomics, and artificial intelligence (WHO, 2019).

Title: Salutare Dialogue for MDTs					
Authors	[name], [name], [name]	Ver.2		Date Authorised	22/01/2025

Clinicians participating in the study will engage with the Salutare One Referral software by initiating patient referrals to the MDT through a structured workflow facilitated by the platform. Upon logging into Salutare One Referral using their secure NHS accounts, they are guided through the process of creating referrals, leveraging instructional videos and software-provided completion instructions.

The platform automatically populates essential patient data from the NHS Spine, including demographics. Doctors supplement this data by inputting specific clinical information pertinent to the referral, such as details about the reason for referral, recent test results, and any additional context that could aid in MDT decision-making.

Once a referral is submitted, MDT panel members utilise the platform to engage in virtual discussions with their colleagues as part of pre-MDT preparation. This collaborative environment allows them to share and review essential patient information, including medical histories, laboratory results, and radiology examinations, all seamlessly integrated into the platform. Salutare One Referral ensures that MDT panel members have comprehensive access to the necessary clinical data required for informed decision-making.

During MDT meetings facilitated by One Referral panel members actively contribute to discussions on patient cases, aided by the platform's capabilities to standardise and automate aspects of the referral and review process. As part of this process, doctors complete the risk scores of the respective MDTs including, for example, the ASA and SORT scores for each patient.

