10.4. Post intervention phase

Prospective review of complex cases discussed by the MDT will be completed.

11. Study Assessments

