Where possible and informative, we will provide both time-series and aggregate data. For instance, while the percentage of re-presented cases will be reported as an aggregate figure, we may also track the absolute number of re-presentations per MDT meeting as a time series to identify any trends. This multi-faceted approach to data reporting significantly strengthens the study design and allows for a more comprehensive evaluation of the Salutare One Referral software's impact. By incorporating time-series data where applicable, we observe learning effects, showing how users' proficiency evolves throughout the intervention period, while also allowing us to detect any fatigue effects or declining engagement over time. Regular data collection helps us assess the Hawthorne effect, determining whether participants' behaviour changes due to being observed and if this effect diminishes. Furthermore, the post-intervention phase data will reveal any carryover effects, indicating whether the software's impact persists after its use is discontinued (Friedman, Wyatt & Ash, 2022).

Title: Salutare Dialogue for MDTs					
Authors	[name], [name], [name]	Ver.2		Date Authorised	22/01/2025

13. Schedule of interventions and assessments

Complex case MDTs (Stanmore Anaesthetics and Royal Free Colorectal Cancer)

	Day 0	Day 1 - 28	Day 29 - 42	Day 42	Day 43 - 98	Day 98	Day 99 - 126	Day 126
Baseline survey	x							
Pre-intervention period		x						
Onboarding period			x					
Onboarding survey				x				
Intervention period					x			
Intervention survey						x		
Post-intervention period							x	
Post-intervention survey								x

High-volume MDTs (Breast Cancer)

	Day 0	Day 1 - 14	Day 15 - 28	Day 28	Day 29 - 56	Day 56	Day 57 - 70	Day 70
Baseline survey	x							
Pre-intervention period		x						
Onboarding period			x					
Onboarding survey				x				
Intervention period					x			
Intervention survey						x		
Post-intervention period							x	
Post-intervention survey								x

High-volume MDTs (Breast Cancer)

	Day 0	Day 1 - 14	Day 15 - 28	Day 28	Day 29 - 56	Day 56	Day 57 - 70	Day 70
Baseline survey	x							

Pre-intervention period		x						
Onboarding period			x					
Onboarding survey				x				
Intervention period					x			
Intervention survey						x		
Post-intervention period							x	
Post-intervention survey								x

14. Study duration

The total duration of the study will depend on the frequency of MDT meetings and the number of cases discussed.

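### At RNOH, and less so at colorectal, cases referred on One Referral by Day 98 but discussed from Day 99 fall in the post-intervention control, so the carryover reading can mix direct exposure with persistence

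*Protocol*

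**What the plan says.** - **Role of the last phase.** Section 1 (Duration of study) defines it as "Post-intervention period (after-study control) with no access to the Salutare One Referral software". Section 12 gives it an inferential purpose: "the post-intervention phase data will reveal any carryover effects", meaning whether the software's impact lasts once its use has stopped.
- **Timing.** The section 13 schedule for RNOH and colorectal runs the intervention over Days 43 to 98 and the post-intervention period over Days 99 to 126. No gap separates the two.
- **Which cases count.** For these two MDTs, section 8.5 states that "all cases discussed during the study pre-intervention, intervention and post-intervention phases will be included in the study analysis". Section 10.4 describes the last phase only as: "Prospective review of complex cases discussed by the MDT will be completed". Both refer to discussion, not referral.
- **When exposure begins.** Section 10.3 has clinicians create the referral on the platform. After submission, "MDT panel members utilise the platform to engage in virtual discussions with their colleagues as part of pre-MDT preparation". Both steps come before the meeting.
- **Volumes.** Section 6 has RNOH meeting fortnightly: "The MDT typically addresses a maximum of 10 complex cases per session". It has colorectal meeting weekly with about 30 cases. For RNOH, section 1 (Target) says: "We aim to collect data for approximately 40 cases discussed without the Salutare One Referral software".

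The protocol does not say how a case referred on the platform before switch-off and discussed after it is to be flagged, excluded or reassigned.

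**The concern.** Carryover, as section 12 uses the term, is an effect that remains when the software is no longer used. A case whose referral was built and prepared on One Referral has had direct use of it, even if the meeting takes place after access ends. If such a case counts as post-intervention, its fuller referral information looks like persistence.

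The outcome most exposed is completeness of pre-assessment information (secondary endpoint 2), and within it the content entered on the referral form, such as medical history. Time from referral to definitive decision (endpoint 8) is touched less: only its starting point is fixed on the platform, and neither size nor direction can be given. What is at stake is a secondary, descriptive statement about whether gains last after withdrawal.

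**Working it through.** **1. Meetings and cases per phase** (sections 6 and 13). The phases are 28, 56 and 28 days long. Cases = (phase days / days between meetings) × cases per meeting.

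| MDT | Interval | Cases per meeting | Pre | Intervention | Post |
|---|---|---|---|---|---|
| RNOH | 14 days | 10 (maximum) | 2 × 10 = 20 | 4 × 10 = 40 | 2 × 10 = 20 |
| Colorectal | 7 days | about 30 | 4 × 30 = 120 | 8 × 30 = 240 | 4 × 30 = 120 |

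**2. Reproducing the stated targets.** At RNOH, cases without the software = 20 + 20 = 40 and cases with it = 40, matching the targets of about 40 and 40. The pre-intervention phase alone gives 20, so the target is reached only if post-intervention cases count as cases without the software. At colorectal the same sum gives 120 + 120 = 240 without and 240 with, against stated targets of 120 and 120. There the pre-intervention phase alone supplies 120, so the inference about how post-intervention cases are counted is available only for RNOH.

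**3. Which post-intervention cases were referred by Day 98.** Let the first post-intervention meeting fall on Day 98 + d and let the lead time from referral to discussion be L days. A case at that meeting was referred by Day 98 if d ≤ L. A case at the next meeting was referred by Day 98 only if d + cycle ≤ L. Since d is at least 1, that cannot happen when L is at most one cycle. For L between 0 and one cycle:

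- RNOH: 0 to 10 of 20 cases (0% to 50%).
- Colorectal: 0 to 30 of 120 cases (0% to 25%).

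L is not in the protocol, so this range is an assumption. At L = 0 the share is zero; at a full cycle it is one whole meeting. Longer lead times would raise it. At colorectal, for example, a 14-day lead would reach two of the four meetings (60 of 120).

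**4. Effect on the carryover reading.** For a measure fixed entirely at submission, with no true persistence, apparent carryover = share × software effect. With an assumed gain of 20 percentage points:

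- RNOH: 20 × 0 to 20 × 0.50 = 0 to 10 points.
- Colorectal: 20 × 0 to 20 × 0.25 = 0 to 5 points.

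**5. Re-presented cases at RNOH.** Section 6 says: "Approximately 20% of cases necessitate re-presentation due to missing critical information". If those from the last intervention meeting return at the next one, 10 × 0.20 = 2 of 20 post-intervention cases (10%) were first referred on the platform. If the software halves the rate, it is 1 of 20 (5%). These counts do not depend on L, but they only identify boundary cases and are not part of the estimate in step 4.

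**The case against.** **Classifying boundary cases belongs in the SAP.** Often it does, and section 8.5 is by itself only an inclusion rule. The objectives and targets are also worded by use of the software, so a platform-referred case is not clearly one without it. But the protocol includes cases by discussion phase and states the carryover inference without qualification. Followed as written, those two statements give the mixture described.

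**Completeness is not all set at submission.** This stands. Section 8.4 makes the presence of risk scores a key completeness indicator, and section 10.3 describes scoring in its account of the meeting. A reader might infer that the whole completeness endpoint is affected; the text supports that mainly for referral-form content.

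**Re-presented cases do not show a bias.** This also stands. A reader might take the 2 of 20 as inflating carryover. Those cases return because information was missing, so they are not shown to carry the software's completeness gain.

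**The boundary may be empty in practice.** Section 10 calls the phase durations indicative and ties them to meeting frequency. Unreviewed referrals might have to be resubmitted locally once access ends. Either could bring the share to zero, but the protocol states no resubmission rule.

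**Per-meeting reporting would reveal it.** Section 12 provides for this where it is informative. At colorectal, if only the first meeting is affected, three clean meetings (about 90 cases) remain. At RNOH there are only two post-intervention meetings, and a fall from the first to the second fits both direct exposure and fading persistence.

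**The reading is weak anyway.** Sections 8.3 and 8.6 call the study a pilot, with 8.6 saying it is not powered to evaluate secondary outcomes comprehensively. The Day 126 survey assesses gains and losses after withdrawal without relying on case allocation. This limits the severity but does not remove the ambiguity.

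**Conclusion.** The point holds in limited form. At RNOH, and to a lesser extent at colorectal, the discussion-phase rule lets cases referred and prepared on One Referral enter the post-intervention control, so the carryover statement can mix direct exposure with true persistence. It applies mainly to referral-form content.

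The share is unknown: 0 to 10 of 20 at RNOH and 0 to 30 of 120 at colorectal, assuming a lead time of at most one meeting cycle, the section 6 caseloads, and no local resubmission of pending referrals. The 10-point and 5-point ceilings further assume a 20-point gain fixed wholly at submission.

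A reader might infer from the RNOH target of 40 that the study's main results are contaminated. The documents do not support that. The target is a collection count, the pre-intervention versus intervention contrast does not use this boundary, and the primary endpoint rests on safety, feasibility and user acceptability. Severity is minor.

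**What to change.** - In the MDT observation dataset, with a sentence in section 8.5, record the route of each case's original referral: One Referral or local form. Capture it prospectively.
- In section 12, base the carryover statement on post-intervention cases submitted on the local form, and report platform-referred cases discussed after Day 98 separately. The route field also identifies re-presented cases.

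A last platform submission date tied to the last intervention meeting, set in sections 10.3 and 10.4, is an alternative for new referrals. Re-presented cases would still need the route field.

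The cost is one data field, one or two sentences, and fewer cases behind a descriptive statement. At RNOH, 20 − 10 = 10 of 20 post-intervention cases remain in the worst case considered, or 20 − 2 = 18 if only re-presentations cross the boundary. At colorectal, 120 − 30 = 90 to 120 remain, counting new referrals only. If platform-referred cases also left the RNOH count of cases without the software, it would fall from 40 to 38 in the re-presentation case, or to 30 in the worst case.

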16.1 NICE and DH requirements for Digital Health Technologies

The One Referral software is classified as a Digital Health Technology (DHT) to be commissioned for use in the health and social care system. The design of this study follows standards for evaluating the effectiveness of Digital Health Technologies (DHTs) as outlined in the Evidence Standards Framework for Digital Health Technologies (NICE, 2019) developed in collaboration with NHS England, NHS Digital and other stakeholders. The framework classifies DHTs by function and stratifies them into evidence tiers based on the potential risk to users.

One Referral is functionally classed as a 'system service' aimed to improve system efficiency and unlikely to have direct and measurable individual patient outcomes. Consequently, it has been classified as Tier A: DHT with potential system benefits but no direct user benefits. This pilot has been designed to generate best practice evidence standard required by the NICE framework to generate evidence of safety, efficacy, and a value proposition to users. As part of this study, we will investigate and evaluate the system's effectiveness on the duration of the patient pathway, from referral to MDT discussion to the decision outcome implementation, e.g. surgery.

Minimum evidence standard:

- DHT performs its intended function to the scale needed

Title: Salutare Dialogue for MDTs					
Authors	[name], [name], [name]	Ver.2		Date Authorised	22/01/2025

- DHT meets Government accessibility requirements

Best practice evidence standard:

- Published evidence that DHT has a plausible mode of action that is viewed as useful and relevant by professional experts or expert groups in the relevant field
- Relevant clinical or social care professionals working in the UK health and social care system have either been involved in designing, developing or testing the DHT
- Published evidence to show that representatives from intended user groups were involved in the design, development or testing of the DHT and to show that users are satisfied with the DHT

Salutare Limited abides by the principles of good practice outlined in 'A guide to good practice for digital and data-driven health technologies (DH, 2019 as updated).

16.2 Clinical safety

Salutare, the manufacturer of One Referral, is committed to meeting the highest standards of patient safety in respect of the use of the One Referral software. The Chief Investigator, [name], has the lead accountability for scientific conduct of the study. [name] acts as the Clinical Safety Officer (CSO) for Salutare Limited having completed the required Clinical Risk Management Training (e-learning and CSO course) provided by NHS Digital. [name] provides clinical safety expertise and oversight, leads the development of Salutare clinical safety processes and documentation, signs off documentation, and oversees compliance with the required standards.

Salutare Limited has developed a 'Clinical Safety Management System', defining a systematic process for the identification of risk and mitigating actions, in compliance with the requirements set out by the clinical risk management standards referred to as DCB0129 and DCB0160. These standards, applicable to Health IT Systems for use within the health and care environment, are mandated under section 250 of the Health and Social Care Act 2012.

Potential risks have been identified and analysed via a review of potential hazards. A Clinical Hazard Workshop has been completed and Clinical Safety Case Report produced. The Clinical Safety Case Report authorises the One Referral deployment in this research study.

